1. INTRODUCTION

The text in the Statistical Analysis Plan (SAP) reflects the analysis methods planned as of the date of the SAP. It contains more details for the analyses mentioned in the Clinical Investigational Plan (CIP) and may be amended to reflect any additional analyses planned prior to unblinding the data.

2. STUDY OBJECTIVES

2.1 Primary Objective

The primary objective of this study is to evaluate the antimicrobial efficacy of 3M™ SoluPrep™ Preoperative Skin Preparation (SoluPrep) by demonstrating non-inferiority to 3M™ SoluPrep™ Film-Forming Sterile Surgical Solution (SoluPrep FF), an FDA-approved active control, with a 0.5 margin (\log_{10} scale), and demonstrating a superiority to saline, the negative control, with a superiority margin of $1.2 \log_{10}/\text{cm}^2$. In addition, both active products should demonstrate persistence of effect where the 6-hour post-treatment measurement is lower than or equal to the observed study day baseline measurement for 100% of the subjects.

2.2 Secondary Objectives

Safety will also be evaluated based on the incidence of adverse events reported during the study and assessment of skin irritation ratings.

CDT

3. INVESTIGATIONAL PLAN

3.1 Study Design

This is a randomized, controlled, third-party blind, single-center study in healthy volunteers where each subject receives 2 of the 3 possible study products on the groin. The study staff performing the bacterial enumeration and the statistician performing the analysis will be blinded to the study products.

3.2 Randomization

The left and right test areas on the subject's inguinal region will be assigned according to a computer-generated randomization schedule where each will receive 1 of the 3 study products (see Table 1). Treatment randomization will be balanced between left and right sides. There are 3 different possible combinations of treatments. These are shown below in Table 2.

To provide enough subjects to meet study objectives, the treatment combinations will be randomized in a 6:1:1 ratio for combinations 1 through 3, respectively, at the single recruiting clinical facility. The details of block size will be documented in the final study report.

Baseline and post-prep samplings at 10 minutes and 6 hours will be randomized to three sites within each test area. The same test site randomization will be used on the left and right sides of a subject's body to reduce the possibility of sampling errors.

The Investigator is responsible for ensuring that the study randomization is followed. Randomization envelopes will be provided to the study site.

CDT

Table 1 Study Products

Treatment Code	Study Product	Description
SP	SoluPrep	Contains 2% w/v chlorhexidine gluconate (CHG) and 70% v/v isopropyl alcohol (IPA). 10.5-mL applicator, tinted.
SPFF	SoluPrep FF	Contains 2% w/v chlorhexidine gluconate (CHG) and 70% v/v isopropyl alcohol (IPA) in combination with an acrylate copolymer. 10.5-mL applicator, tinted.
S	Saline	Negative control. Sterile 0.9% saline. 20-mL bottle.

Table 2 Subject Treatments

Treatment Combination	Left and Right Treatment
1	SoluPrep 10.5-mL and SoluPrep FF 10.5-mL (SP + SPFF)
2	SoluPrep 10.5-mL and saline (SP + S)
3	SoluPrep FF 10.5-mL and saline (SPFF + S)

Randomization Plan:

A 3M statistician not assigned to the project will develop a randomization program and generate the randomization code list. The code list will include randomization number, left side treatment, right side treatment, baseline sample site, 10-minute sample site and 6-hour sample site. The randomization assignments will be printed and inserted into security envelopes then tightly sealed.

The Data Manager will strip the treatment assignment from the programs that are used to download the data from Clindex®. This will keep the statistician assigned to the study blinded until data lock.

CDT

Randomization Process:

For each eligible subject to be randomized, the investigator or designee will do the following:

- Retrieve a randomization envelope with smallest available randomization envelop number.
- Record randomization number onto a Data Collection Sheet (DCS) and/or the electronic Case Report Form (eCRF).
- When the treatments are applied, record onto a DCS and/or the eCRF; left side treatment applied, right side treatment applied, baseline sample site, 10-minute sample site and 6-hour sample site.
- Subjects will continue to be randomized until a minimum of 100 observations (with a baseline that meets the Treatment Day requirement) from each of the active treatments and 30 observations from the saline control (with a baseline that meets the Treatment Day requirement) have been collected.

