6.2 Determination of Sample Size

The Final Monograph (21 CFR Part 310 Safety and Effectiveness of Health Care Antiseptics; Topical Antimicrobial Drug Products for Over-the-Counter Human Use) calls for a minimum of 100 observations per treatment. A standard deviation of 1.0 \log_{10}/cm^2 was observed in study EM-05-012760. One-hundred subjects per treatment arm

CDT

provides 94% power using a non-inferiority margin of $0.5 \log_{10}/\text{cm}^2$ with a 1-sided alpha of 0.025.

In the same study, a superiority to the negative control was observed to be approximately $2.5 \log_{10}/\text{cm}^2$, with a lower 95% confidence bound of $2.26 \log_{10}/\text{cm}^2$. A sample size of 30 for the negative control will ensure that the mean for \log_{10}/cm^2 reduction of skin flora relative to Treatment Day baseline will be normally distributed. With 100 observations for the active products and 30 observations for the negative control, the mean observed difference must be greater than $1.62 \log_{10}/\text{cm}^2$ for the lower 95% confidence bound to be greater than $1.2 \log_{10}/\text{cm}^2$. At these sample sizes and the lower 95% confidence bound of $2.26 \log_{10}/\text{cm}^2$, there is 79% power to show superiority to the negative control with a 1-sided alpha of 0.025.

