8. EFFICACY ANALYSIS

8.1 Primary Efficacy Analysis

The average treatment effect (ATE) for the investigational product will be estimated using a linear regression of the 10-minute post-treatment bacterial count (\log_{10} scale) on the additive effect of a treatment indicator and the baseline measurement (\log_{10} scale). The lower bound of the 95% confidence interval for the additive treatment effect must not include the investigational product being more than $0.5 \log_{10}/\text{cm}^2$ lower than the positive control.

The ATE of the test product compared to the negative control is estimated as the contrast of treatment effect of negative control minus the treatment effect of the test drug in the linear regression. Likewise, the ATE of the active control compared to the test product is estimated as the contrast of treatment effect of test product minus the treatment effect of the active control in the linear regression. Superiority to negative control uses a margin of $1.2 \log_{10}/\text{cm}^2$, which would be demonstrated by a lower bound of the 95% confidence interval for the contrast to exceed $1.2 \log_{10}/\text{cm}^2$.

An example code for the analyses specified above is shown below:

Proc Mixed data=D_14624.LogMicro;

Class Treatment;

CDT

```
Where Timepoint=1 and Treatment in (1 2);  
Model LogRecovery=Treatment LogBaseline/ddfm=kr;  
Lsmeans Treatment/cl;  
Run;
```

The percent of samples for which the 6-hours post treatment recovery is lower than the baseline recovery will be calculated by active product. Thus, if \log_{10} reduction is >0 the sample has not returned to baseline. The Final Monograph requires that these percentages be 100.

An example code for percentage return to baseline is shown below:

Proc Format;

```
value Return      -5-0='Returned to Baseline'  
                 0.0001-8='Did not Return to Baseline';  
run;
```

Proc Freq data=D_14624.LogMicro;

```
Where Timepoint=2;  
Tables LogReduction*Treatment/nopercent norow;  
format LogReduction return.;
```

Run;

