### 3.3 Randomization and Blinding

The left and right test areas on the subject's inguinal region will be assigned according to a computer-generated randomization schedule to receive 1 of the 3 study products (see Table 3.4.1A). Randomization will be balanced between left and right sides. There are 3 different combinations of treatments. These are shown below in Table 5.3.3A. To provide an ample number of subjects, the treatment groups will be randomized into 10 blocks of 12-2-2 for each of groups 1 through 3, respectively. Baseline and post-prep samplings will be randomized to sites within each test area. The same test site randomization will be used on each side of a subject's body to reduce the possibility of sampling errors. An example of one of the blocks is shown in Table 3.3.1 below.

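### Side is balanced at randomization but absent from the primary model, so the interval is slightly too wide if left and right differ; add side together with a subject effect

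*SAP*

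**What the plan says.** **Design.** SAP 3.1 states that "each subject receives 2 of the 3 possible study products on the groin", one on each side. SAP 3.2 adds that "the treatment combinations will be randomized in a 6:1:1 ratio for combinations 1 through 3".

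**Balance by side.** SAP 3.2: "Treatment randomization will be balanced between left and right sides". Protocol 3.3: "Randomization will be balanced between left and right sides". The example block of 16 in protocol 3.3 shows this inside each combination. SoluPrep is on the left in 6 of the 12 rows of combination 1, and combinations 2 and 3 each split one and one.

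**Recording.** The randomization process in SAP 3.2 has the site record the product applied to each side, so side is known for every observation.

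**Primary model.** SAP 8.1 regresses the 10-minute log10 count "on the additive effect of a treatment indicator and the baseline measurement", and protocol 8.2.1 describes the same regression. The example code in SAP 8.1 has "Class Treatment" as its only class statement and the model line "Model LogRecovery=Treatment LogBaseline/ddfm=kr". It has no side term and no RANDOM or REPEATED statement.

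**The concern.** When allocation is forced to balance on a factor, the treatment contrast is protected from that factor by design. The usual practice is to put the factor in the model as well, so that its variation is removed from the error term. If it is left out, the contrast is still protected, but the standard error is calculated as though it were not. The trial then carries the restriction without taking the precision it offers.

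What is at stake is a little width in the 10-minute intervals that are compared with the 0.5 log10 non-inferiority margin and the 1.2 log10 superiority margin. There is a smaller second point. SAP 5.2 judges each side's baseline separately, and protocol 1.5 expects 15% of subjects to miss the Treatment Day baseline requirement. Exact side balance may therefore not survive into the modified intent-to-treat set, and a side term would guard against what imbalance remains.

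**Working it through.** **Inputs from the documents.** 100 observations per active product, SD 1.0 log10/cm², margin 0.5, one-sided alpha 0.025 and stated power 94% (SAP 6.2); allocation 6:1:1 (SAP 3.2).

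**Assumptions, because neither document gives a figure.** Left/right difference d in the 10-minute log10 count, taken from 0.1 to 0.5 with 1.0 as an extreme. Within-subject correlation rho, taken as 0.5 where it is needed.

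**Step 1. Reproduce the plan's power.** For two independent samples, SE = 1.0 × √(2/100) = 0.1414. Power = Φ(0.5/0.1414 − 1.96) = Φ(1.576) = 94.2%, or 94.0% with the noncentral t on 198 degrees of freedom. The stated 94% reproduces. It is an independent-samples figure, which matches a model without a subject term.

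**Step 2. Omit side from the planned model.** With side balanced and coded ±½, a difference d contributes variance d²/4 to the residual. The percentage below is relative to a variance of 1.0. Whether the SD of 1.0 already contains a side difference is not stated, so power is shown both ways, starting from 94.24%.

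| d (log10) | d²/4 | Power with side added, if SD 1.0 includes d: SD becomes √(1 − d²/4) | Power with side omitted, if SD 1.0 excludes d: SD becomes √(1 + d²/4) |
|---|---|---|---|
| 0.1 | 0.25% | 94.29% | 94.19% |
| 0.2 | 1.00% | 94.45% | 94.04% |
| 0.3 | 2.25% | 94.70% | 93.78% |
| 0.5 | 6.25% | 95.46% | 92.92% |
| 1.0 | 25% | 98.31% | 88.54% |

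The cost is about 0.2 points at d = 0.2, 0.5 at d = 0.3 and 1.2 to 1.3 at d = 0.5.

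**Step 3. Bias and coverage.** Simulation with 120 subjects at 6:1:1, 15% of sides dropped at random without replacement, and 2,000 runs per setting:

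- The mean error of the contrast with side omitted was at most 0.01 log10 in every setting, including d = 1.0.
- At d = 0.5 and rho = 0, the model's SE was 0.155 without side and 0.150 with it. The actual SD of the estimate without side was 0.152. The stated SE therefore errs on the large side.
- Coverage of the 95% interval in that setting was 95.65% without side and 94.95% with it. Simulation error on each is √(0.95 × 0.05/2000), about 0.5 points.
- When the 0.5 difference was also present at baseline, the SE was 0.151 without side and 0.150 with it. The baseline covariate took up much of it.

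**Step 4. Compare with the missing subject effect.** At rho = 0.5 and d = 0, the planned model's SE was 0.150 against an actual SD of 0.124, with coverage of 98%. The SE is overstated by a factor of 0.150/0.124 = 1.21. Omitting side at d = 0.5 raises the SE by only 0.155/0.150 = 1.03.

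**Step 5. Omit side once a subject effect is fitted.** For subjects who receive both active products, the within-subject difference has variance 2(1 − rho) when SD is 1.0, and omitting side adds d². The inflation is d²/(2(1 − rho)). At rho = 0.5 this is 0.04/1 = 4% for d = 0.2 and 0.09/1 = 9% for d = 0.3, or about 2% and 4.4% on the SE.

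**The case against.** The strongest reply is that nothing goes wrong. Balance by design keeps the contrast free of material bias, the interval errs on the safe side for both non-inferiority and superiority, and the power lost at modest d is a fraction of a point. The side difference itself is undocumented. The protocol fixes no order of working by side, and it numbers the sites as mirror images (5.3.3.1) and uses the same site randomization on both sides (3.3), which makes the sides more alike. All of this stands. It limits the gain, but it does not remove the case for a term that costs one degree of freedom and matches the randomization.

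A reader might infer three stronger things that the documents do not support:

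- **That the 4% and 9% inflations apply to the plan as written.** They describe a within-subject comparison. SAP 8.1 fits no subject effect, so the planned comparison is not paired and the figures are 1% and 2.25%.
- **That any left/right difference stays in the error.** Each side has its own Treatment Day baseline in the model, and this takes up part of a difference already present before treatment.
- **That the non-inferiority or superiority conclusion is at risk of a false positive.** The omission makes the tests slightly harder to pass.

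It is also fair to reply that most of the excess width comes from the missing subject effect. At rho = 0.5 that is correct, and adding side alone would change little.

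**Conclusion.** The point holds as a small improvement. The randomization balances on side, the data record it, and the primary model leaves it out. If the sides differ in a way that baseline does not capture, the interval is slightly too wide, and the error is conservative.

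The size depends on two quantities that the documents do not give. With SD 1.0 and the planned model, the extra residual variance is 0.25% to 6.25% for d from 0.1 to 0.5 log10, and the loss of power stays at or below about 1.3 points. If d is zero there is no gain. The ranking of the subject effect as the larger omission rests on rho being near 0.5; if rho were zero, a subject effect would bring nothing. Exclusion of single sides could disturb the balance, but random loss of 15% of sides produced no material bias in simulation.

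**What to change.** In SAP 8.1, text and example code, add side (left/right) as a fixed class effect together with a subject effect. In the code:

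- put Side and Subject in the class statement next to Treatment;
- add Side to the model line after LogBaseline;
- add either a RANDOM subject term or a REPEATED statement within subject.

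The Kenward-Roger option already in the code would then have a within-subject covariance to work on. Bring the description in protocol 8.2.1 into line, and make the change before unblinding.

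The cost is one degree of freedom for side (120 subjects at 6:1:1 would give 120 × 6/8 = 90 pairs with both active products), a few lines of code and no new data. The two terms should go in together, because side alone recovers little.

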3.3 Blinding

The study products cannot be blinded from the Investigator or study staff performing the product application, sample collection and skin assessment due to the obvious differences in applicator design, color, and other physical characteristics. However, the study staff performing the bacterial enumeration will not be involved in the study product application or the collection of samples and, therefore, will be blinded to the study products. The statistician performing the analysis will also be blinded.

The biostatistician will remain blinded to treatment assignment before database lock and final study data analysis. The treatment assignments will be removed from the relevant databases and random treatment assignments given to each subject. The final data review

CDT

and data classification meeting will be conducted before data lock and statistical programming will occur using the dummy treatment assignments.

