5.3 Per-Protocol Population

A second per-protocol (PP) data set will be defined excluding any subjects with major deviations including lack of compliance

A treatment side will be excluded from the modified intent-to-treat population that has one of the following:

- A treatment side with a compromised dressing at 6 hours
- A subject who was not compliant to study requirements during the time between the 10 minute and 6-hour sample collection

CDT

A treatment side might also be excluded for scrub time or sample times outside of the approved window.

All deviations not captured above that will result in exclusion from the PP analysis will be defined and justified in a blinded fashion. In addition, documentation will be made of these data classification decisions prior to data lock.

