7.2 Protocol Deviations

Protocol deviations are any departure from the protocol. Protocol deviations that affect the evaluability of subjects will be reviewed during a blinded review process and documented before data lock and study analysis. Deviations will be summarized by categories, treatment group and overall. Listing of protocol deviations will also be provided.

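### Nothing in the plan withholds post-treatment counts from the pre-lock exclusion review, and one discretionary exclusion can change the 100% persistence result

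*SAP*

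**What the plan says.** **What is masked.** SAP 3.2: "The Data Manager will strip the treatment assignment from the programs that are used to download the data from Clindex". SAP 3.3: "The treatment assignments will be removed from the relevant databases and random treatment assignments given to each subject". The same section says that the final data review "and data classification meeting will be conducted before data lock and statistical programming will occur using the dummy treatment assignments". Label masking is the only masking described. Neither document says which listings the meeting sees, who attends, or that count values are held back.

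**Who knows the treatments.** SAP 3.3: "The study products cannot be blinded from the Investigator or study staff performing the product application". The same holds for the staff who collect samples and assess skin.

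**What is left to judgement.** SAP 5.3: "A treatment side might also be excluded for scrub time or sample times outside of the approved window". It adds: "All deviations not captured above that will result in exclusion from the PP analysis will be defined and justified in a blinded fashion". SAP 7.2: "Protocol deviations that affect the evaluability of subjects will be reviewed during a blinded review process".

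**Which data set.** SAP 5.2 makes MITT the primary efficacy set, with fixed rules: baseline between 5.00 and 7.50 log10/cm², and recovery data present. SAP 5.3 is headed as the PP definition, yet the sentence that introduces its list of exclusions says that sides are removed from MITT. Protocol 8.3 describes MITT and the full randomized set and mentions no PP set.

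**The criterion at stake.** SAP 8.1 counts, for each active product, the sides whose 6-hour recovery is below baseline: "The Final Monograph requires that these percentages be 100".

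**The concern.** Masking codes protects a decision only if the codes are what would bias it. For the persistence endpoint they are not. A failure is a comparison of two counts from the same side, and anyone who holds both counts can see it under any code. If a side that failed also has a late sample, a doubtful scrub time or a deviation not yet classified, the plan lets the group decide at that point whether the side stays in.

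The criterion is all-or-nothing, so one such decision settles the result for a product in whichever data set it applies to. Even if every decision were made in good faith, the final report could not show that exclusions were independent of outcome. Identification of saline sides from their high counts is a secondary matter.

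**Working it through.** **1. The plan's own figure.** SAP 6.2 gives 94% power for non-inferiority with 100 per arm, SD 1.0, margin 0.5 and one-sided alpha 0.025. Standard error = 1.0 × √(2/100) = 0.1414. Power = Φ(0.5/0.1414 − 1.96) = Φ(1.576) = 0.942. The figure reproduces, so the SAP's inputs are used below.

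**2. What one side does to persistence.** With 100 sides of one product, one failure gives 99/100 = 99.0%, which misses the criterion. Without that side the result is 99/99 = 100%.

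The documents give no true failure rate per side, so a range for q is assumed. With n = 100 and independent sides:
- P(pass) = (1 − q)^100
- P(pass if one failure can be removed) = (1 − q)^100 + 100q(1 − q)^99

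| assumed q | pass, no removal | pass, one removable |
|---|---|---|
| 0.1% | 90.5% | 99.5% |
| 0.5% | 60.6% | 91.0% |
| 1% | 36.6% | 73.6% |

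The last column is an upper limit. It supposes that a lone failing side always has some ground for exclusion and that the ground is always used.

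**3. Non-inferiority.** In simulated samples of 100 normal values with SD 1.0, dropping the 1, 3 or 5 highest recoveries lowers the mean by 0.025, 0.068 or 0.106 log10. Against the 0.5 margin this is small.

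**4. Can saline sides be recognised?** Inputs from SAP 6.2: difference d = 2.26 (lower bound) to 2.5 (observed), SD 1.0, taken here as the spread of one side's 10-minute value.
- In a pair *known* to contain saline, with independent sides, the higher count is the saline side with probability Φ(d/√2) = 0.945 to 0.961. With an assumed within-subject correlation of 0.5 it is Φ(d) = 0.988 to 0.994. With SD varied from 0.8 to 1.5 (assumed) and independent sides, it is 0.86 to 0.99.
- For a side taken alone, with 30 of 230 sides saline, the best cut lies d/2 + ln(200/30)/d above the active mean. It finds 61% to 69% of saline sides, and 79% to 82% of the sides it flags are saline.
- Under the 6:1:1 allocation, 6/8 = 75% of subjects have no saline side, so the single-side figures are nearer to what a reviewer could do.
- If SoluPrep and SoluPrep FF have equal effects, counts cannot tell them apart.

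**5. How much discretion there is.** SAP section 6 gives limits for the 10-minute sample, the 6-hour sample and plating, but none for scrub time. Protocol 5.3.4.1 sets the scrub duration without a tolerance. The scrub-time ground therefore has no stated window to be outside of.

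**The case against.** *Visibility of counts is inferred.* A reader might conclude that the meeting reviews the counts. The documents do not say so. They are silent on the meeting's listings. Programming under dummy codes suggests real counts with scrambled labels, but that is inference. What stands is that nothing withholds them.

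*The primary analysis uses MITT, whose rules are fixed.* This is the strongest objection. The open-ended clause in SAP 5.3 is expressly limited to PP, and SAP section 8 attaches no decision rule to PP. A reader might infer that the primary persistence verdict can be changed by discretion; on the natural reading it cannot. The objection is incomplete only because SAP 5.3 literally names MITT for the listed exclusions, and the permissive timing sentence follows that list.

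*The two listed exclusions are mandatory and recorded early.* Dressing failure and non-compliance lead to exclusion without choice. Compliance is queried before the 6-hour sample (SAP 7.4), dressing loss is recorded when the site is sampled (Protocol 5.3.3.4), and plates incubate for 72 hours (Protocol 5.3.4.1). This stands. The exposure lies in the timing clause and in deviations classified later.

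*Blinding here means blinding to treatment.* SAP 3.3 uses the term that way, and decisions are justified and documented before lock. So the plan does not contradict itself. The point is that treatment blinding is the wrong protection for a label-free outcome.

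*Recognising saline changes little.* Persistence is judged on the active products, and a failing side may itself be saline. This stands and is why saline identification is secondary.

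**Conclusion.** The concern holds in limited form, as a cheap improvement. Masking is described for labels only, some exclusions are discretionary, and a 6-hour failure can be read without a label. One exclusion in about 100 sides can therefore change 99.0% to 100% for a product in the affected data set. That set is PP on the natural reading, with MITT not clearly protected until SAP 5.3 is reworded.

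The size depends on an unknown failure rate. At an assumed 0.5% per side, the chance that one product passes rises from 60.6% to at most 91.0%.

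A reader might go further and infer that saline is reliably unmasked or that non-inferiority is at risk. The documents' figures do not support either. The 94% to 96% recognition rate applies only to pairs already known to contain saline, and the shift in a mean is about 0.11 log10 or less for up to five dropped sides. Nothing here suggests that anyone intends to misuse the discretion.

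**What to change.** In SAP 3.3, 5.3 and 7.2:

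- State that classification is completed and signed on listings of deviations, recorded times, dressing status, compliance answers, baseline counts, and flags showing that 10-minute and 6-hour data are present, with the post-treatment count values withheld. The flags are needed because MITT membership depends on them.
- Name the meeting's members, and state that staff who know the treatments do not vote on exclusions.
- State that count queries are resolved separately by data management before lock.
- Replace the permissive timing clause with a fixed rule tied to the 10-minute and 6-hour sampling limits in SAP section 6. Either state a scrub-time limit or drop scrub time as a ground.
- Reword SAP 5.3 so that its exclusions define PP and leave MITT, the primary set, unchanged.

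**Cost.** Some variables are dropped from the review listings and a few sentences change. Treatment assignment is already stripped from the downloads, so the mechanism exists. Count queries move outside the meeting, and pre-lock programming uses dummy count data or waits for sign-off. Sample size, endpoints and the analysis model are unchanged. If counts are already withheld in practice, one sentence in SAP 3.3 settles the masking part; the timing rule and the population wording still need correction.
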